Zooplankton and phytoplankton samples will be collected using 64 µm and 20 µm mesh sizes plankton net respectively. Then the plankton will be homogenized using Sted Fast homogenizer (Fisher Scientific Co.). A portion of the homogenized materials will be inoculated into alkaline bile peptone enrichment media and incubated overnight and then plated onto thiosulphate citrate bile salt sucrose (TCBS) agar and tellurite taurocholate gelatin agar (TTGA). The inoculated plates will be incubated at 37°C for 18 to 24 hours. Vibrio-like organisms (from colony appearance) will be picked up and streaked on gelatin agar medium (Monsur, 1961) and incubated at 37°C to determine the production of gelatinase and will be inoculated into Kliglers Iron Agar (KIA) and Motility Indole Urea (MIU) agar. Presumptive vibrio isolates will be checked for lysine and ornithine decarboxylase, arginine dihydrolase and for fermentation of mannitol, sucrose, mannose and arabinose and growth in 0.3, 8 and 10% NaCl. Serology will be done if indicated. Isolation and

identification of *V. cholerae* O1 and O139 will be carried out following the procedures described by Islam *et al.* (1990a, 1990b, 1994b).

Three hundred milliliter of water sample will be filtered through 0.20 µm Millipore filter paper and the filter paper will be enriched in alkaline bile peptone in 120 ml glass bottle and will be incubated overnight at 37°C. Then the rest of the procedures will be followed as described above.

Direct Fluorescent Microscopy (DFA)

All the samples will be tested for both *V. cholerae* O1 and O139 by fluorescence microscope following the procedures described by Hasan *et al.* (1994, 1995). The procedures are briefly described below.

A thin smear of 5-µl of resuspended sample will be prepared on a well. Controls will be run simultaneously. 5-µl of absolute ethanol will be added in control or sample well to fix the smear, again will be air dried. 10-µl of reconstituted DFA reagent will be added to each well. The slides will be placed in a covered, moist

chamber, and will be incubated at 37°C for 30 ± 5 minutes protecting from light. Then the slides will be rinsed thoroughly with PBS protecting from light. Excess moisture will be absorbed using a blotting paper. A drop of fluorescent mounting medium will be added on the slide and covered with a 22 x50mm, No. 1 cover slip. For best results, the slides will be read immediately at a magnification of 1000 X with oil immersion. The slides will, however, be kept cool, in the dark, or will be kept humid to prevent drying.

Colony blot hybridization technique

Preparation of colony blots and hybridization will be carried out according to published procedures (Wright *et al.* 1992 and Maniates *et al.* 1982). Environmental water samples will be plated directly or upon appropriate 10 fold serial dilutions on non selective LB agar plates and incubated overnight at 37°C. Colonies will be transferred to a Whatman # 541 filter paper from the culture plates. The filters will be transferred with colony side up on to # 3 Whatman filters that are pre-soaked with denaturation solution (4 ml) for 10 minutes. The filter paper will be saturated with neutralizing solution (4 ml) for 3 min then the filter will be air dried and soaked in pre hybridization buffer at 42°C for 1 hour. Then hybridization will be carried out with DIG labelled ctx probe at 42°C for over night. Then the washing, blocking and signal detection will be carried out following the procedures provided by the manufacturers (Boehringer Mannheim, Japan).

Physicochemical parameters of water

Physicochemical measurement will be made at the time of collection at each sampling site. This will include water temperature, pH (Orion Portable pH Meter, Cat. No. 210 A, Orion Research, USA), salinity, total dissolved solids and conductivity (HACH Conductivity Meter, Cat. No. 51800-18, Sension™ 5, HACH Company, USA) and dissolved oxygen content (HACH Dissolved Oxygen Meter, Cat. No. 51850-18, Sension™ 6, HACH Company, USA). All these readings will be taken in the field using potable meters. The free CO₂, hardness and chloride will be measured in the laboratory following standard procedures (APHA, 1998). The number of hours of sunshine, total rainfall and the ambient temperature will be obtained from the Metrological Department of Bangladesh in Dhaka.

Clinical surveillance

Data on the incidence of cholera in Matlab, Bangladesh will be collected from the Matlab Hospital records of ICDDR,B.

Activities in Mozambique:

Like Bangladesh, environmental samples will be collected from both lotic (open water, e.g., river, canal, sea etc.) and lentic (closed water, e.g., pond, lake, wells etc.) environment of Beira, Mozambique. Phytoplankton, zooplankton and water samples will be collected every two weeks interval. The samples will be transported to the CHAEM laboratory following standard procedures and processed following the same procedures as described in Bangladesh part. The isolation and identification of *V. cholerae* O1 and O139 will be carried out following enrichment technique as described in material and methods section in Bangladesh part. The VBNC *V. cholerae* O1 and O139 will also be detected using direct fluorescent antibody technique. All these methodologies will be set up in CHAEM laboratory by ICDDR,B as a part of technology transfer. Samples will be processed and preserved for detection of *V. cholerae* O1 and O139 by colony blot hybridization from the environmental samples. Preparation of colony blots will also be carried out in CHAEM and the dried blots will be sent to ICDDR,B for hybridization using DIG labelled probe.

The stool sample from the patients having watery diarrhoea from Infectious Diseases Hospital in Beira will be tested by dark field microscope as well as by using culture technique at CHAEM. The information about the patient will be taken from the record of Infectious Diseases Hospital.

The phytoplankton, zooplankton and chemical analysis will be carried out at CHAEM in Beira following the methods described in Bangladesh part.

Facilities Available

Describe the availability of physical facilities at the place where the study will be carried out. For clinical and laboratory-based studies, indicate the provision of hospital and other types of patient's care facilities and adequate laboratory support. Point out the laboratory facilities and major equipment that will be required for the study. For field studies, describe the field area including its size, population, and means of communications. (TYPE WITHIN THE PROVIDED SPACE).

The sampling sites will be selected at Matlab, a field study area of ICDDR, B located 70 km southeast of Dhaka in a low lying deltaic region. All the cholera patients from the sampling sites will be reported to the hospital for treatment. We will be able to know the time of cholera epidemic from the hospital records.

All the environmental samples will be processed in the Environmental Microbiology Laboratory in Dhaka. All the techniques required for testing the environmental samples are already in place in this laboratory with adequate manpower and expertise. All the equipments are also available in this laboratory.

Data Analysis

Describe plans for data analysis. Indicate whether data will be analyzed by the investigators themselves or by other professionals. Specify what statistical software packages will be used and if the study is blinded, when the code will be opened. For clinical trials, indicate if interim data analysis will be required to monitor further progress of the study. (TYPE WITHIN THE PROVIDED SPACE).

The isolation and enumeration of *V. cholerae* O1 and O139 from various environmental samples by culture, FA, and colony blot hybridization will be related with the physicochemical parameters of water and the seasonality of cholera. The data from Bangladesh will be compared with the data from Mozambique to find out the role of environmental factors in the seasonality and endemicity of cholera in these two countries.

Logistic regression analysis will be done to do the qualitative analysis (i.e., the presence and absence of *V. cholerae* O1 and O139 using culture technique). For quantitative analysis, Poisson regression analysis will be used.

The biweekly data from both the lotic and lentic environment will be analyzed by first computing the percentage of samples positive by FA, conventional culture and colony blot hybridization by site combination using McNemar test (Sokal and Rohlf, 1989).

A two-way analysis of variance will be performed with site and month as the effects in the model and model assumptions will be determined by examining residuals for normality following the procedures described by Sokal and Rohlf (1989).

The correlation of association between phytoplankton and zooplankton with *V. cholerae* will be analyzed using Pearson's correlation method.

Ethical Assurance for Protection of Human Rights

Describe in the space provided the justifications for conducting this research in human subjects. If the study needs observations on sick individuals, provide sufficient reasons for using them. Indicate how subject's rights are protected and if there is any benefit or risk to each subject of the study.

No human subject is involved in this environmental study.

Use of Animals

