The sampling at Beira, Mozambique for the analysis of cholera ecology will include the sea, river, well water, and other surface water bodies. Basic water chemistry tests at sites will include conductivity, pH, temperature, salinity, dissolved oxygen and total dissolved solids. In the laboratory we will analyze free carbon dioxide, chlorides and hardness. Tests for *V. cholerae* will include culture by enrichment technique to (qualitative) assess the presence of vibrios in water, phytoplankton and zooplankton. Faecal coliforms in water will be counted by the membrane filtration technique; fluorescent microscopy will indicate the non-culturable vibrios, alive or dead. Colony blots will provide the detailed quantitative assessment of vibrios in the sample. All of these tests will be carried out every 15-day interval throughout the study. The CHAEM laboratory at Beira has been selected as the main base for developing capacity and for carrying out some of the microbiological analysis for this research. Procedures will be set up as part of the future monitoring system. In course of time, the more routine laboratory procedures will also eventually be enhanced at Quelimane and Maputo. Equipment for chemical and microbiological testing used in this research will remain with the centre at Beira after completion of the project.

Phase II: Like Bangladesh, if it is found in the first phase of the study that phytoplankton and zooplankton are also acting as reservoirs of cholera in Mozambique, then environmental cholera intervention strategy will be introduced using capulanas as a filtering device in the second phase. The intervention study will be carried out in two phases. The first phase study will be in-depth laboratory-based investigation to find out the effectiveness of capulanas to remove phytoplankton and zooplankton associated *V. cholerae* O1 and O139. In the second phase, acceptability and effectiveness of capulanas will be investigated in the community to reduce cholera incidence.

After successful completion of the first phase, which includes the identification of risk factors of cholera and its environmental intervention, attempts will be made in the second phase to focus on the identification of the risk factors for other infectious diseases in Mozambique particularly for Shigellosis.

Environmental monitoring

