At 15-day intervals, various environmental samples will be collected including water, phytoplankton and zooplankton for three years. A three-year study will provide the data needed to obtain statistically valid results and conclusions. One-time sampling will be done for consecutive ten days and weekly for one month to find out whether there is any day-to-day or weekly variation in pathogen load. As we plan to collect sample every 15 days interval, 26 samples from each kind from each site will be collected in a year. Apart from being logistically feasible, this sample size will permit us to demonstrate two-log reduction in the count of microbes in each site. Two water systems (one lentic and one lotic) at Matlab will be selected for sampling. A total of 468 (26 X 2 X 3 =156 each of phytoplankton, zooplankton and water) samples will be collected. All the samples will be transported to Dhaka and will be processed within 24 hours of collection. Culturable and VBNC *V. cholerae* O1 and O139 will be isolated, counted and detected following conventional culture, colony blot and fluorescent antibody techniques. The procedures to be followed are described below:

Sample collection and Processing

Phytoplankton

One litre water from aquatic environment will be collected in a 1 litre capacity narrow mouth Nalgene plastic bottle with 3 ml Lugol's iodine solution for the qualitative and quantitative analysis of phytoplankton. Bottles will be kept in a dark undisturbed place at room temperature for 48 to 72 hours for sedimentation of phytoplankton. Concentrated phytoplankton will carefully be collected from the bottom of the bottles in 100ml vials. If the abundance is low, the phytoplankton will be concentrated by passing through plankton net of mesh size 20µm and then will be kept in a 4-oz bottle. The concentrated phytoplankton samples will be preserved by adding 4% formalin. Then the samples will be kept for identification and enumeration.

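### The Matlab sample counts (26 a year, 156 per type, 468 in total) do not follow from the stated 15-day interval, and the interval for Beira is stated in two ways

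*Protocol*

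**What the plan says.** The Environmental monitoring section sets the schedule: "At 15-day intervals, various environmental samples will be collected including water, phytoplankton and zooplankton for three years". It then derives a yearly count from that interval: "As we plan to collect sample every 15 days interval, 26 samples from each kind from each site will be collected in a year". The count is applied to two sites: "Two water systems (one lentic and one lotic) at Matlab will be selected for sampling". The total follows: "A total of 468 (26 X 2 X 3 =156 each of phytoplankton, zooplankton and water) samples will be collected".

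These figures cover Matlab only; no sample count is given for Beira. The same paragraph relies on this sample size when it says that a two-log reduction in microbial counts can be shown at each site.

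The interval for Beira appears in two places. The Methods section, after describing the Beira sampling and tests, says: "All of these tests will be carried out every 15-day interval throughout the study". The section on activities in Mozambique says: "Phytoplankton, zooplankton and water samples will be collected every two weeks interval". The Data Analysis section calls the series from lotic and lentic waters biweekly.

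**The concern.** The protocol presents 26 a year as a consequence of sampling every 15 days, which it is not. The Environmental monitoring section gives the 15-day interval twice, so it cannot be put down to one stray word. The three-year totals inherit the mismatch, and they are the only sample size in the protocol.

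At stake is whether the plan can be carried out as written. Field staff who follow the interval will not reach the stated totals; staff who work to the totals must depart from the stated interval. At Beira there is no total from which to infer the intended schedule, and the two statements of the interval differ. The comparison between countries depends on two laboratories working to one plan, so that plan should be unambiguous.

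**Working it through.** **Inputs from the protocol.** Interval 15 days; 26 samples per kind per site per year; 2 Matlab water systems; 3 years; 3 sample types (phytoplankton, zooplankton, water). For Beira: 15 days (Methods) and two weeks (activities in Mozambique).

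**Step 1: the plan's own figure.**
- Per type: 26 × 2 sites × 3 years = 156.
- In total: 156 × 3 types = 468.

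The multiplication is right. The question is where 26 comes from.

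**Step 2: dates per year = 365 / interval.**
- At 15 days: 365/15 = 24.3.
- At 14 days: 365/14 = 26.07.
- Interval implied by 26 a year: 365/26 = 14.04 days.

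**Step 3: three-year totals (3 × 365 = 1,095 days).**

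| Schedule | Dates per site | Per type (× 2 sites) | Total (× 3 types) | Against 468 |
|---|---|---|---|---|
| As stated | 78 | 156 | 468 | – |
| 15 days, number of intervals (1,095/15) | 73 | 146 | 438 | 30 fewer, 6.4% |
| 15 days, both end points counted | 74 | 148 | 444 | 24 fewer, 5.1% |
| 14 days (1,095/14) | 78.2 | 156.4 | 469.3 | agrees |

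Using 365.25 days a year changes nothing material: 15 days then gives 24.35 a year and a total of 438.3. Of the two intervals that the protocol names, only 14 days reproduces 26, 156 and 468.

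**Step 4: the effect on precision, if 15 days is literal.** Treating samples as independent, standard errors scale with the square root of the ratio of sample sizes:
- 146 instead of 156: √(156/146) = 1.03.
- 148 instead of 156: √(156/148) = 1.03.

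Both are about 3% wider. The effect on the two-log statement cannot be calculated, because the protocol gives no standard deviation, significance level or power for it.

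**Step 5: Beira.** Set side by side, the Methods section has 15 days, the Mozambique section has 14, and Data Analysis has biweekly. Read as every two weeks, biweekly agrees with the second and not with the first.

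**The case against.** The best defence is that the authors meant a fortnight throughout and wrote 15 days loosely. The figures 26, 156 and 468, the two-week wording for Mozambique and the term biweekly all fit that reading. If it is right, the sample size is correct and only the words need changing. This has real weight: a reader might infer that the sample size is overstated and that 468 will not be reached, but the documents do not establish that. What remains is that 15 days and 26 a year cannot both hold.

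A reader might also infer that Matlab on 15 days and Beira on 14 would drift apart, by 26 days after 26 rounds, and spoil the comparison between countries. The documents do not support this either. The Methods section puts Beira on 15 days, as at Matlab, and the Mozambique section introduces its sampling as being like that in Bangladesh. Data Analysis contains no fortnight-paired or fixed-lag analysis between countries. Its analysis of variance uses month as an effect, and both intervals give about two dates a month (24.3/12 = 2.0; 26.07/12 = 2.2).

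Nor is it an error that the total leaves out the check on short-term variation, described as "One-time sampling will be done for consecutive ten days and weekly for one month". The product behind 156 is shown openly and covers the routine series. The protocol does not say which sites or sample types the extra sampling covers. Even if it were done at both sites for all three types, it would not explain the stated total: 73 + 10 + 4 = 87 dates, and 87 × 2 × 3 = 522, not 468.

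**Conclusion.** The inconsistency is real and can be checked by arithmetic. The stated 15-day interval gives about 24.3 dates a year, while the stated counts require 14 days. Taken literally, 15 days gives 438 to 444 samples at Matlab rather than 468, about 5% to 6% fewer, with standard errors about 3% wider at most. The range reflects whether both end points are counted. It assumes three full years, two sites, three sample types and no missed visits; the precision figure also assumes independent samples. For Beira, the protocol separately states two different intervals and no count.

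The documents do not show which element is the slip, so this is a disagreement between interval and count and not a demonstrated loss of samples. It is small in statistical terms. It is still worth correcting, because it affects the only stated sample size and the working schedule at both sites.

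**What to change.** State one sampling interval for both countries, in the same words, in the Methods, Environmental monitoring and Mozambique sections, and derive the counts from it. There are two consistent choices:

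- **Every 14 days.** This agrees with the Mozambique and Data Analysis sections and keeps 26 a year, 156 per type and 468 in total. It costs about 5 more sampling rounds per site over three years than a true 15-day schedule (78 − 73 = 5).
- **Every 15 days.** Change the Mozambique wording to match, and restate the Matlab totals as about 73 dates per site, 146 per type and 438 in total. Derive these from the three-year period. Rounding first to 24 a year would give 24 × 3 = 72 dates, 144 per type and 432 in total, which again would not match the interval.

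Under the second choice, the term biweekly in Data Analysis should also be changed. Apart from the extra rounds in the first choice, the cost is a few words of text.

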normally isolated from <1% of water samples during epidemics, 12% of water samples in their study of 92 water samples from ponds, lakes, rivers, and canals in rural Matlab and urban Dhaka yielded *V. cholerae* O139. Therefore, environmental surveillance of *V. cholerae* O139 along with *V. cholerae* O1 will also be carried out in both Mozambique and Bangladesh. The Governments of Mozambique and Bangladesh are committed to reducing their diarrhoeal disease burdens and keen that the most appropriate and effective approaches and methods are used in cholera prevention and control.

Cholera research during the last twenty years has progressed understanding of the disease but the prevalence of cholera cases continues to be very high. The accumulated findings of this work indicates that incidence of the disease is now potentially much more predictable and preventable than hitherto realized. However, relatively little has been done to apply this knowledge to those regions that continue to suffer the highest burden of the disease. Furthermore, no predictive model has yet been developed that can be offered to local government environment and health departments as a tool for prevention. One key to progress in understanding cholera risks is that *V. cholerae* was more recently found to be resident in environmental reservoirs where there are the right physical and chemical conditions, and that it is associated with other micro-organisms that can be easily removed from water.

Indication of some of the chemical environmental influences was offered as an explanation for differing patterns of incidence of cholera in coastal cities during work carried out on environment, health and population displacement in Mozambique (Collins, 1993a, 1993b, 1996a, 1996b). More microbiologically detailed work carried out by ICDDR,B through a number of extensive studies in Bangladesh explains how environmental reservoirs of *V. cholerae* are influential on incidence of cholera (Islam *et al.*, 1993a, 1994a,

1994b, 1994c, 1994d, 1997). More specifically, this has confirmed that *V. cholerae* is resident in the aquatic environment of Bangladesh. Its survival is dependent on key environmental characteristics including levels of alkalinity, salinity, and microbiological flora and fauna that play a crucial role in its ecology and transmission to people who become infected.

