In epidemiological and ecological study in Bangladesh for the last 5 years, it has been observed that phytoplankton and zooplankton can act as microhabitat for *V. cholerae* O1 in the aquatic environment of Bangladesh (Table. 1). We do not know whether similar situation exists in Mozambique.

[figure not shown]

Fig. 6. Relationship between incidence of cholera and rainfall in Mozambique

[figure not shown]

Fig. 7. Seasonal dynamics of pH and water temperature in a fresh water lake in Bangladesh, compared rainfall and the number of cholera cases in the surrounding area. Note that the peak in cholera cases follows the peak in rainfall and coincides with a temperature peak.

Table 1: Isolation of culturable *V. cholerae* O1 from the various components of aquatic environments of Bangladesh during 1999 to 2002

Components	Total number of samples	Total number of isolates
Water	1923	21
Zooplankton	1923	12
Phytoplankton	1923	12
Water Hyacinth	758	2

It has been observed that the seasonality of cholera in Bangladesh is also associated with the seasonality of plankton bloom formation in the aquatic environment of Bangladesh (Islam *et al.*, 1994b). The multiplication of the phytoplankton and zooplankton in the aquatic environment is also related with the changes of various physicochemical parameters of water (Islam *et al.*, 1994b). As phytoplankton is the food for zooplankton, the phytoplankton bloom is followed by the zooplankton bloom. It is not known whether similar changes of the physicochemical parameters of water in the cholera endemic areas of Mozambique also take place during cholera seasons, Therefore in the present study a comparison of all these factors will be considered.

Studies have also shown that the toxigenic *V. cholerae* during association with the aquatic plants do not lose their pathogenic properties (Islam *et al.*, 1990a, 1990b, 1993b) but after certain times become nonculturable (Colwell and Huq, 1994; Colwell *et al.*, 1996; Islam *et al.*, 1990a, 1994b; Huq *et al.*, 1990). These viable and noncultureable *V. cholerae* have been detected both in association with the blue green algae and zooplankton from the aquatic environment in Bangladesh (Islam *et al.*, 1994b; Huq *et al.*, 1990). Therefore attempts will be made to see whether *V. cholerae* also remains in association with the plankton in the aquatic environment of Mozambique in viable but noncultureable (VBNC) form.

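### The sample size is justified by a two-log reduction that no Phase I analysis tests, and at the protocol's own O1 isolation rates culture positives at Matlab will be too few for multi-covariate regression

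*Protocol*

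**What the plan says.** The Environmental monitoring section sets the sampling at 15-day intervals over three years and states that "26 samples from each kind from each site will be collected in a year". Two Matlab water systems are sampled, giving 156 samples of each component and 468 in all. Apart from feasibility, the reason given for this number is that "this sample size will permit us to demonstrate two-log reduction in the count of microbes in each site".

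The Methods text describes the initial phase as a test of whether environmental influences on cholera ecology are similar in the two countries. The cloth-filter intervention is placed in Phase II and depends on what Phase I finds.

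The Data Analysis section says "Logistic regression analysis will be done to do the qualitative analysis", defining that analysis as presence or absence of O1 and O139 by culture. It adds Poisson regression for quantitative data, a McNemar comparison of detection methods, a site-by-month analysis of variance and Pearson correlation.

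The Background gives two sources for O1 culture rates. Table 1 reports isolations "from the various components of aquatic environments of Bangladesh during 1999 to 2002". The text also says that O1 is "normally isolated from <1% of water samples during epidemics", against 12% for O139 in one study of 92 water samples.

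**The concern.** A sample-size statement should name the quantity that the study will estimate or test. Here it names a fall in microbial counts within a site, but nothing is applied in Phase I to lower the counts and no analysis compares counts before and after anything. A reader cannot tell from it what the study can detect about plankton as a habitat or about physicochemical influences, which are Aims 2 and 3.

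The only binary regression specified uses culture results, and the protocol's own data show that culturable O1 is rare. If almost no samples are positive, a regression on several water measurements gives estimates that are unstable or separated. A run of zero isolates would also exclude little. Neither limit is stated, so the protocol promises more from the O1 culture data than they can deliver.

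**Working it through.** **1. The plan's own count.** 26 per year × 2 sites × 3 years = 156 per component; × 3 components = 468. Both figures reproduce. Per site and component, 26 × 3 = 78.

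**2. The two-log statement.** It cannot be reproduced, because the groups compared, alpha, power and standard deviation are not given. As an illustration only, assume that one year's 26 samples are split 13 against 13, with δ = 2 log10 and two-sided alpha 0.05. Power = Φ(δ / (SD × √(2/13)) − 1.96):
- SD 1: 99.9%
- SD 2: 72%
- SD 3: 40%

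80% power needs an SD of at most 2 / (2.80 × √(2/13)) = 1.82. The statement could be true or false depending on the SD. These figures also need quantifiable counts in most samples, which is doubtful for O1 if only about 1% are culture positive.

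**3. O1 culture rates (Table 1).**
- Water: 21/1923 = 1.09%
- Zooplankton: 12/1923 = 0.62%
- Phytoplankton: 12/1923 = 0.62%

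The table counts isolates, so the number of positive samples can only be the same or smaller.

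**4. Expected positives (n × p) and chance of none ((1 − p)^n).**

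| Component | 78 samples (one site) | Chance of none | 156 samples (both sites) | Chance of none |
|---|---|---|---|---|
| Water | 0.85 | 42% | 1.70 | 18% |
| Zooplankton | 0.49 | 61% | 0.97 | 38% |
| Phytoplankton | 0.49 | 61% | 0.97 | 38% |

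With exact 95% limits on the Table 1 rates, the expectation per site is 0.53–1.30 for water and 0.25–0.85 for each plankton type. A strict 15-day interval gives 365/15 ≈ 24 samples a year; the expectations then fall to 0.79 and 0.45.

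**5. Everything pooled.** 156 × (21 + 12 + 12)/1923 = 3.65 expected O1 positives in 468 samples. Treating the three components as independent binomials, the chance of five or more is about 30% and of ten or more about 0.4%. Even two covariates would leave 3.65/2 ≈ 1.8 events each.

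**6. O139 in water at the quoted 12%.** 78 × 0.12 = 9.4 per site; 156 × 0.12 = 18.7 over both sites.

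**7. What zero would mean.** The two-sided 95% upper limit for 0/n is 1 − 0.025^(1/n):
- n = 78: 4.6%, about four times the Table 1 water rate and seven times the plankton rate.
- n = 156: 2.3%, about twice the water rate and nearly four times the plankton rate.

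**The case against.** Several points on the other side stand.

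- **The regression is not impossible.** A reader might infer that the logistic model cannot be fitted at all. The documents do not support that. The model also covers O139, which at 12% would give about 9 water positives per site, enough for a very small model. The protocol does not say that models are fitted separately by site and component, and it fixes no covariate list; that detail may properly sit in an analysis plan. Pooled O1 data would most likely contain a few events.
- **The two-log figure is not shown to be unattainable.** Under a modest SD it would be easily detected. A seasonal fall in counts is a conceivable meaning, but no such comparison is named. The fault is that the claim is not tied to any Phase I question.
- **Culture is not the only outcome.** The protocol expects low culturability and already plans fluorescent antibody, colony blot and Poisson analyses. These may give more positives, but the logistic analysis is defined on culture.
- **Beira.** A reader might predict that a zero there would be taken as absence of a reservoir. The protocol says no such thing, gives no Beira sample count or Mozambique isolation rate, and plans antibody testing there too.
- **The short intensive sampling.** A reader might extend the argument to "One-time sampling will be done for consecutive ten days and weekly for one month". That exercise concerns pathogen load, which need not be measured by culture, so the O1 culture rates do not settle it.

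**Conclusion.** The concern holds in a limited form. The two-log sentence does not justify the sample size for what Phase I sets out to learn: it has no matching hypothesis, intervention, analysis or inputs. Separately, at the protocol's own O1 rates the culture-based logistic regression at Matlab would rest on fewer than one expected positive per site and component (water could slightly exceed one within the uncertainty of Table 1) and about 3.7 in all. That is too few for useful multi-covariate O1 estimates, and O1 is the organism named in the hypothesis and in Aim 3.

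This assumes that the 1999–2002 Bangladesh rates apply to the two Matlab sites, that samples behave as independent, and that isolates approximate positive samples; if they differ, positives are fewer. O139 in water may support a small model if the 12% from one study of 92 samples carries over to all seasons and to these sites. Nothing can be computed for Beira.

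**What to change.** - In Environmental monitoring, replace the two-log sentence with the real precision: 78 samples per site and component; about 0.85 O1 culture positives expected in water and 0.49 in each plankton type at the Table 1 rates; two-sided 95% upper limit 4.6% if 0/78 and about 2.3% if 0/156.
- In Data Analysis, report O1 culture positivity descriptively with exact confidence intervals, or limit modelling to single-covariate Firth logistic regression.
- Base multivariable modelling on the fluorescent-antibody or colony-blot outcomes already collected. The protocol gives no positivity rate for either, so the number of covariates should be settled once the number of positives is known.
- State that finding no culture isolates does not exclude a reservoir at the Bangladesh rate.

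This changes wording and analysis only and needs no extra samples. The price is that the stated capability becomes less favourable. The multivariable results would also describe a different outcome from culture: the protocol itself notes that fluorescence microscopy shows non-culturable cells whether alive or dead.
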